### **8.2 Sample Size and Accrual**

07-H-0005

[name].

February 3, 2021

Amendment AA

Using the current overall proportion of clinically significant oral chronic GVHD of 0.25, we note that with 36 patients per arm we would have 80% power to detect the same difference of 30% (15% versus 45%) when testing the difference of proportions at a significance level of 0.05. With amendment R (version date 5-6-2016), we thus propose to reduce the required sample size to 72 subjects. We aim to achieve this new accrual goal within two years and we plan to reassess the futility of protocol if we cannot enroll the expected number of subjects.

**Drop-outs:** In order to maintain appropriate statistical power, subjects who prematurely go off study (i.e. are non-compliant with study requirements or develop oral GVHD in the period between baseline assessments and first dose of study drug) will be replaced. To account for a possible drop-out rate of up to 10%, up to 82 subjects may be accrued. Safety data on drop outs will be included in the safety analysis.

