The incidence of chronic GVHD in the placebo group was originally estimated as 0.6 based on the published literature. The reported incidence varies from 38 to 83% depending on the type of stem cell transplantation (as shown in the table below). Peripheral blood stem cell (PBSC) transplantation had a higher incidence of chronic oral GVHD compared to bone marrow transplantation. At our institute, we use peripheral blood stem cell as a stem cell source. However there are different protocols utilizing T-cell depleted peripheral stem cell transplantation which provides similar T cell dose (10-H-0154) or even a smaller T cell (06-H-0248, 12-H-0028) dose as the ones used in bone marrow grafts. Furthermore, most literature reported the incidence of chronic oral GVHD irrespective of its severity. Busca et al. (Haematologica 2005; 90: 567) reported up to 62.5% of chronic oral GVHD were graded as moderate to severe (equivalent to grade 3 or higher). Therefore, the incidence of clinically significant (grade 3 or higher) oral chronic GVHD at day 90 after randomization, a primary endpoint of this study would be potentially around 40%, much lower than 60%.

Author	Journal	N	Study population	Incidence of chronic oral GVHD
Flowers	Blood 2002; 100: 415	95	Adult bone marrow or PBSC	Bone marrow 70% PBSC 83%
Busca	Haematologica 2005; 90: 567	104	Adult bone marrow	All grade oral GVHD 38% (62.5% had moderate to severe chronic oral GVHD)
Treistner	Biol Blood Marrow Transplant 2005; 11: 721	49	Pediatric bone marrow	45%
Pavletic	Am J Hematol 2005; 78: 265	87	Adult bone marrow or PBSC	Bone marrow 53% PBSC 70%

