### 3. STUDY DESIGN

This is a pilot Phase II, randomized, double blind, prospective, parallel group study. Consenting subjects between 90 and 100 days post hematopoietic stem cell transplantation and without evidence of oral chronic 07-H-0005 8  
[name].  
February 3, 2021  
Amendment AA

GVHD will be randomized 50/50 to dexamethasone 0.01% or placebo oral rinse. Subjects will be evaluated at monthly intervals during the 3 months of active prophylaxis and 6 months after the intervention period is completed. Development of clinically significant oral chronic GVHD will serve as the primary endpoint and be defined in this study as objective score of 3 or higher on Lichen Planus Severity Scale (Appendix C).

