## **8. BIOSTATISTICAL CONSIDERATIONS**

### **8.1 Hypothesis**

#### **8.1.1 Primary hypothesis**

Our primary hypothesis is that dexamethasone oral rinse 0.5 mg/5 ml administered 3 times a day for 2 minutes will decrease the incidence of clinically significant oral chronic GVHD (primary endpoint) over the three month treatment period.

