### 8.5 Data Analyses

This study will be analyzed according to the “intent to treat” principle, that is, all randomized subjects will be included. Subjects not evaluated for endpoints will be considered to have reached the primary endpoint. Every effort will be made to reach and evaluate the subjects at the monthly intervals and at the end of the 3 month intervention period. The differences in proportions of significant oral chronic GVHD will be assessed by a chi-squared test (with continuity correction). Treatment group differences in the severity scores, pain and xerostomia scores, and quality of life scores (OHIP-14) will be assessed using the Wilcoxon test. Adjustments will be made for age and other covariates of interest, such as systemic immunosuppression. Adverse events will be tabulated by severity and treatment assignment. For pediatric subjects, analyses will include growth assessment (growth chart [length for age, weight for age percentiles

and body mass index] for age percentiles) and bone age and the associated z-scores (the number of standard deviations the child's measures [weight, height etc] differ from the population mean).

The intervention period will be 3 months. Should the subject reach the primary endpoint (development of clinically significant oral chronic GVHD), the subject will be asked to participate in end of study assessments and then will go off study. Subjects who did not develop oral chronic GVHD in the intervention phase of the study will be followed for up to 6 months to document late development of oral chronic GVHD. All subjects will be evaluated after 6 months after completion of the intervention phase of the study in the absence of clinical oral GVHD. Final statistical analysis will be performed once all subjects in the sample have completed the study and all records have been collected. We will use stratified analyses to account for effects of systemic immunosuppressive agents and other prognostic factors.

In the event of a protocol violation, the aggregate data will be analyzed with and without those subjects involved in the incident.

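### The 80% power in section 8.2 holds for an uncorrected two-sided test; the continuity-corrected chi-squared test fixed in 8.5 has about 74% if two-sided, and the 15%/45% rates are not reconciled with the overall 0.25

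*Combined protocol and SAP*

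**What the plan says.** Section 8.2 (Sample Size and Accrual) states that "with 36 patients per arm we would have 80% power to detect the same difference of 30% (15% versus 45" (percent), "when testing the difference of proportions at a significance level of 0.05". It names no test statistic, sidedness or continuity correction. On this basis Amendment R lowers the required sample to 72, with up to 82 accrued to allow for up to 10% drop-out.

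Section 8.5 (Data Analyses) fixes the primary comparison: differences in the proportion with significant oral chronic GVHD "will be assessed by a chi-squared test (with continuity correction"). It also adopts intention to treat with the rule "Subjects not evaluated for endpoints will be considered to have reached the primary endpoint". It gives no sidedness either. Section 8.1.1 words the primary hypothesis in one direction: the rinse "will decrease the incidence of clinically significant oral chronic GVHD".

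On the event rates, 8.2 opens with "Using the current overall proportion of clinically significant oral chronic GVHD of 0.25" and then uses 15% and 45%. Section 3 says subjects "will be randomized 50/50 to dexamethasone 0.01% or placebo oral rinse". Section 2.2 gives 60% as the original placebo-group estimate and argues that the incidence of clinically significant disease "would be potentially around 40%, much lower than 60" (percent).

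**The concern.** A stated power should belong to the test that will be run. The continuity correction makes the chi-squared test more conservative, and at 36 per arm the loss of power is noticeable. If 8.2 left the correction out and 8.5 applies it, the trial is less likely to detect its target effect than the plan says, and a null result would be read against a claimed 80% that the analysis does not deliver. The reduction to 72 subjects rests on this one sentence.

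The rates raise a second, smaller question. A reader who sees an overall 0.25 and equal allocation expects the two design rates to average 0.25. They average 0.30, and the plan does not say why.

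**Working it through.** **Inputs.** n = 36 per arm, p1 = 0.15, p2 = 0.45, significance level 0.05 (8.2); equal allocation (section 3); corrected chi-squared test (8.5). Two-sided testing is assumed unless noted.

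**Step 1: reproduce the plan's figure (uncorrected, two-sided).**
- Mean rate: (0.15 + 0.45)/2 = 0.30.
- Standard error under the null: √(2 × 0.30 × 0.70/36) = 0.1080.
- Standard error under the alternative: √((0.15 × 0.85 + 0.45 × 0.55)/36) = 0.1021.
- Power = Φ[(0.30 − 1.960 × 0.1080)/0.1021] = Φ(0.865) = 80.7%.
- At 35 per arm the same formula gives 79.5%. The required n is 35.4, rounded up to 36.

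The plan's 36 per arm and 80% are therefore exactly the uncorrected two-sided answer.

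**Step 2: the test in 8.5 (corrected, two-sided).** With equal arms the correction reduces the absolute difference by 1/n = 1/36 = 0.0278.
- Power = Φ[(0.30 − 0.0278 − 1.960 × 0.1080)/0.1021] = Φ(0.593) = 72.3%.

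**Step 3: exact check.** Sum the binomial probabilities of all 37 × 37 possible tables in which the statistic exceeds the critical value (3.841 for chi-squared two-sided; z = 1.645 in the favourable direction one-sided).

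| Test, 36 per arm, 15% vs 45% | Formula | Exact |
|---|---|---|
| Uncorrected, two-sided | 80.7% | 82.0% |
| Corrected, two-sided | 72.3% | 74.2% |
| Corrected, one-sided 0.05 | 82.3% | 83.3% |

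**Step 4: n per arm for 80% with the corrected two-sided test.** The formula gives 41.8, so 42 per arm (84 in total, above the ceiling of 82). By exact calculation, power is 79.0% at 40 per arm and 80.4% at 41.

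**Step 5: the rates.** 15% and 45% average 0.30. A 30-point difference centred on 0.25 is 10% versus 40%. For that pair at 36 per arm, the corrected two-sided test has 77.5% power by formula and 80.0% exact.

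Two harmless readings of 0.25 are possible. Both need figures that the documents do not give.
- *Chance.* If 15%/45% is true, the probability of a pooled rate of 25% or less is 38%, 31% or 23% when it rests on 24, 36 or 60 subjects (assumed numbers).
- *Evaluated subjects only.* If 0.25 leaves out non-evaluated subjects, whom 8.5 counts as events, a non-evaluated fraction m gives an overall rate of m + (1 − m) × 0.25. That equals 0.30 at m = 6.7% and 0.325 at m = 10%.

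**The case against.** **Sidedness is open.** Section 8.2 names no test, and 8.1.1 is directional. A one-sided 0.05 corrected test has 82% to 83% power, so the stated 80% is not wrong on every reading. This stands as a condition on the conclusion. The two-sided reading is still the more likely one: it is the natural meaning of a chi-squared test, and 36 is exactly the two-sided uncorrected minimum, whereas the one-sided minima are 28 (uncorrected) and 35 (corrected). If one-sided testing was intended, 8.2 needs to say so.

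**The ceiling of 82 covers the gap.** With 41 evaluated subjects per arm, exact power is 80.4%. But 8.2 provides the extra subjects to replace drop-outs, and 8.5 keeps all randomized subjects and counts the non-evaluated as events, which narrows the difference. If 15%/45% applies to evaluated subjects and 10% of each arm is not evaluated (an assumption), the rates become 23.5% and 50.5%, and exact corrected power is about 66% at 41 per arm and 57% at 36. The ceiling does not restore 80%.

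**The shortfall is specific to 15%/45%.** At 10%/40%, which fits both the overall 0.25 and the 40% in 2.2 if that is a placebo rate, the planned test reaches 80.0% exact. This is true and lowers the practical weight, but 15%/45% is the pair that 8.2 states.

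**The 0.25 is not an error.** A design alternative need not match an observed pooled rate. This stands: the point is a request for explanation only.

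**It is a pilot phase II trial.** That limits the consequences, but the plan still states a power and fixes a test, and the two should agree.

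**Conclusion.** The concern holds. The 80% in 8.2 is right for an uncorrected two-sided test and does not describe the test in 8.5. Read as two-sided, the planned test has 74.2% power exact (72.3% by formula) at 36 per arm for 15% versus 45%. The chance of missing the target effect is about 26% rather than the nominal 20%; like for like, 25.8% against 18.0% exact, or 27.7% against 19.3% by formula.

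This rests on two-sided testing and on 15% and 45% being the rates as analysed, with non-evaluated subjects already counted as events. One-sided testing would remove the shortfall; non-evaluated subjects on top of those rates would deepen it. There is no bias and no inflation of type I error.

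The use of 15%/45% beside an overall 0.25 is an unexplained inconsistency, not a proven error. The whole point should be fixed, but it does not undermine the trial.

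**What to change.** In 8.2, restate the power for the test in 8.5, for example: *With 36 subjects per arm, the two-sided 0.05 chi-squared test with continuity correction has about 74% power (exact calculation) for event rates of 15% versus 45%, where non-evaluated subjects are counted as events.* This names the test, the sidedness, the method and the meaning of the rates. If a one-sided test is intended, state that in both 8.2 and 8.5 and give its power instead.

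Add one sentence on what the 0.25 is based on, whether it counts non-evaluated subjects, and why 15%/45% is kept. Alternatively, use rates that average 0.25: 10%/40% gives 80.0% exact, or 77.5% by formula, with the corrected two-sided test.

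The cost is one or two sentences and a less favourable stated power. No extra patients and no change of test are needed. Dropping the correction in 8.5 would also align the sections, at 82.0% exact power and an exact two-sided size of about 4.6% to 5.3% at 36 per arm for common rates of 15% to 45% (about 2.2% to 2.8% with the correction). That would change the primary test, so it should be considered only before unblinding.

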### **8.3 Primary Endpoint**

The primary objective of this study is to evaluate the safety and efficacy of topical dexamethasone 0.01% solution used as an oral rinse for prevention of oral chronic graft versus host disease. The primary endpoint is the proportion of subjects that develop clinically significant (severity score 3 or higher) oral chronic GVHD by three months post dexamethasone administration. For the purposes of this study, oral chronic GVHD with the objective score of 3 or higher on a 6-point oral GVHD scale (Appendix C) will be considered clinically significant. An intention to treat analysis will be conducted as the primary analysis.

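### Replacing early leavers only partly protects power when 8.3 and 8.5 keep them in the primary analysis, and the plan gives two different times for randomisation

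*Combined protocol and SAP*

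**What the plan says.** **Replacement and power.** Section 8.2 gives 80% power at 36 per arm for 15% versus 45% at a 0.05 level, 72 subjects in all. It starts from "Using the current overall proportion of clinically significant oral chronic GVHD of 0.25" and does not say whether that figure, or the 15% and 45%, counts unevaluated subjects as events. It then says "In order to maintain appropriate statistical power, subjects who prematurely go off study" will be replaced. Its examples are non-compliant subjects and those with oral GVHD between baseline and first dose. On numbers: "To account for a possible drop-out rate of up to 10%, up to 82 subjects may be accrued". For drop-outs it mentions only the safety analysis.

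**Primary analysis.** Section 8.3: "An intention to treat analysis will be conducted as the primary analysis". Section 8.5 says that "all randomized subjects will be included" and adds: "Subjects not evaluated for endpoints will be considered to have reached the primary endpoint". The test is a chi-squared test with continuity correction.

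**Randomisation time.** Section 6.1.1 places consent and randomisation last in a list of assessments made at days 60-90 after transplant. Section 4.3 has pharmacy randomise once eligibility is confirmed and consent given, and names no day. Section 3 describes randomising subjects who are at days 90-100 and have no evidence of oral chronic GVHD. Section 8.8.2 places an oral reassessment at days 90-100, and oral chronic GVHD arising before the first dose takes the subject off study.

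**The concern.** Replacement fully maintains power only if the replaced subject leaves the primary analysis or adds no imputed outcome. Under 8.3 and 8.5 a randomised leaver stays in the denominator beside the replacement and, if unevaluated, is an event. Forcing events at the same rate in both arms raises the lower rate more than the higher one, so the difference shrinks. Section 8.2 gives power for 36 per arm and none for the set of up to 82 that 8.5 would analyse.

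The randomisation time matters because it fixes who is in that set. If assignment comes before the day 90-100 recheck, a subject found there with oral chronic GVHD is already randomised and may count as an event that study drug could not have prevented. If assignment follows the recheck, that subject is never randomised.

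**Working it through.** **Inputs from the plan.** 15% and 45%, 36 per arm, 0.05, 72 subjects, drop-out up to 10%, cap of 82 (8.2); all randomised subjects analysed, unevaluated = event, continuity-corrected chi-squared (8.5); 1:1 allocation (Section 3).

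**Assumptions not in the plan.** Two-sided test; 82 splits as 41 per arm; 15% and 45% are rates among evaluated subjects; loss is equal by arm and unrelated to outcome.

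**Step 1: the plan's own figure.** With pooled rate 0.30 and no continuity correction,

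n = [1.96·√(2·0.30·0.70) + 0.8416·√(0.45·0.55 + 0.15·0.85)]² / 0.30² = (1.2702 + 0.5154)² / 0.09 = 35.4, so 36 per arm.

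Power at 36 per arm is 80.7% by this approximation and 82.0% by exact enumeration, so the stated 80% reproduces for the uncorrected test. With the correction in 8.5, exact power is 74.2%.

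**Step 2: effect of the 8.5 rule on the rates.** If a share m is unevaluated, p′ = p(1 − m) + m, and the difference becomes 0.30(1 − m).
- m = 5%: 0.15·0.95 + 0.05 = 0.1925 and 0.45·0.95 + 0.05 = 0.4775, difference 0.285.
- m = 10%: 0.235 and 0.505, difference 0.270.

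**Step 3: exact power.** Sum the binomial probabilities of all pairs of event counts whose chi-squared statistic exceeds 3.841. For fixed counts, k forced events per arm are added to binomial counts among the remaining n − k.

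| Scenario | Randomised per arm | Uncorrected | Continuity-corrected |
|---|---|---|---|
| No leavers | 36 | 82.0% | 74.2% |
| 5 unevaluated per arm, not replaced | 36 | 63.8% | 50.8% |
| 5 unevaluated per arm, replaced | 41 | 73.7% | 64.3% |
| No unevaluated | 41 | 86.2% | 80.4% |
| 1 unevaluated per arm | 41 | 83.8% | 77.3% |
| 2 unevaluated per arm | 41 | 81.3% | 74.1% |
| 3 unevaluated per arm | 41 | 78.7% | 70.7% |
| Random 5% unevaluated | 41 | 79.6% | 72.6% |
| Random 10% unevaluated | 41 | 73.5% | 65.5% |

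**Step 4: how much replacement recovers.** With 5 unevaluated per arm, uncorrected: (73.7 − 63.8) / (82.0 − 63.8) = 9.9 / 18.2, about 54%. Corrected: (64.3 − 50.8) / (74.2 − 50.8) = 13.5 / 23.4, about 58%.

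**Step 5: the other reading of 15% and 45%.** If those rates already count unevaluated subjects as events, no adjustment applies, and 41 per arm gives 86.2% / 80.4%.

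**Step 6: the randomisation passages side by side.**
- 6.1.1: in the day 60-90 screening step.
- 4.3: after eligibility and consent, no day given.
- Section 3: days 90-100, without oral chronic GVHD.
- 8.8.2: recheck at days 90-100, before first dose.

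6.1.1 and Section 3 cannot both describe the same act, and 4.3 does not settle it. The plan gives no pre-dose case rate. For scale, one forced event per arm at 41 per arm lowers power from 86.2% / 80.4% to 83.8% / 77.3%.

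**The case against.** **Replacement does help.** A reader might infer that it achieves nothing. That is wrong: in the 5-per-arm case it lifts uncorrected power from 63.8% to 73.7%. If the full 82 are accrued, uncorrected power stays above 80% with 2 unevaluated per arm. What stands is that 8.2 promises maintenance without limit.

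**The unevaluated rate may be low.** The 10% in 8.2 is a drop-out ceiling, and a drop-out is not necessarily unevaluated. Pre-dose cases are found by examination, 6.5 and 8.8.2 ask leavers to complete exit assessments, and 8.5 promises every effort to evaluate. Treating the whole 10% as unevaluated is therefore an upper scenario; at 5% the uncorrected shortfall from 80% is negligible.

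**The continuity-corrected column mostly shows something else.** It is already 74.2% at 36 per arm with no leavers. That is a separate mismatch between the sample size calculation and the planned test, and should not be charged to replacement.

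**The timing conflict is narrow.** Section 4.3 cannot be read as fixing days 60-90, and exclusion 4.2.2 refers to infection status by day 90, so eligibility confirmation can run to the edge of Section 3's window. The conflict rests mainly on one list item in 6.1.1 against Section 3. Nor do the documents say outright that a pre-dose case is an event: 8.1.1 refers to the treatment period and 8.3 to three months after administration. Whether it counts is open, but on the 6.1.1 reading that subject is in the all-randomised set.

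**An existing sensitivity analysis does not close the gap.** Section 8.5 says: "In the event of a protocol violation, the aggregate data will be analyzed with and without those subjects involved in the incident". That covers protocol violations only and does not change the primary analysis set.

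**Conclusion.** Both points hold and should be fixed, with moderate confidence in their practical size.

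Replacement may only partly maintain power under the plan's own rules. On the stated assumptions, it recovers a little over half of the loss when 5 per arm are unevaluated. At 41 per arm, uncorrected power falls below 80% between 2 and 3 unevaluated per arm, and is 73.5% at a random 10%. If 15% and 45% already follow the 8.5 rule, there is no loss; 8.2 does not say which applies.

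It is tempting to conclude that the trial is underpowered because of its replacement rule. The documents do not support that, since they give no unevaluated rate and take steps to keep it low. They support only that the assurance in 8.2 does not follow from 8.3 and 8.5. The randomisation time is inconsistent between 6.1.1 and Section 3, which leaves membership of the primary set unsettled for pre-dose cases.

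**What to change.** 1. Reconcile 6.1.1, 4.3, Section 3 and 8.8.2 to one randomisation time point. For subjects not yet assigned, placing it after the day 90-100 recheck, as Section 3 describes, keeps pre-dose cases out of the primary set. Subjects already randomised stay in the ITT set, with any pre-dose cases reported by arm.
2. In 8.2, say that replacement may only partly maintain power, that replaced randomised subjects stay in the ITT set, and whether 15% and 45% count unevaluated subjects as events. Restate power under the 8.5 rule and the planned test, labelled as 5% and 10% unevaluated scenarios.

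The cost is a text amendment, with no added patients or procedures. The downsides are a less favourable stated power and assignment closer to dosing. Step 1 cannot change assignments already made; for those subjects it only makes clear which cases are in the analysis.

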### **8.3 Primary Endpoint**

The primary objective of this study is to evaluate the safety and efficacy of topical dexamethasone 0.01% solution used as an oral rinse for prevention of oral chronic graft versus host disease. The primary endpoint is the proportion of subjects that develop clinically significant (severity score 3 or higher) oral chronic GVHD by three months post dexamethasone administration. For the purposes of this study, oral chronic GVHD with the objective score of 3 or higher on a 6-point oral GVHD scale (Appendix C) will be considered clinically significant. An intention to treat analysis will be conducted as the primary analysis.

